12.5.2. Analyses of the Secondary Endpoints

The key secondary efficacy endpoints are CR rate, OS, CR + CRh rate, and ORR. Additional secondary efficacy endpoints include CR + CRi (including CRp) rate, DOCR, DOCRh, DOR, DOCRi, TTCR, TTCRh, TTR, TTCRi, transfusion requirements (platelet and RBC), rates of infection, days hospitalized, other efficacy and safety measures that are potentially indicative of clinical benefit, change from baseline in QoL assessments, and the rates of CR with IDH1 MC.

Sensitivity analyses and subgroup analyses for the secondary efficacy endpoints will be specified in the SAP.

12.5.2.1. Key Secondary Endpoint Analyses

12.5.2.1.1. Complete Remission Rate

Complete remission rate is defined as the proportion of subjects who achieve a CR. A Cochran-Mantel-Haenszel (CMH) test will be used to compare CR rate between the 2 treatment arms. A logistic regression model will be used to estimate the treatment effect in terms of an odds ratio. The odds ratio and its associated 95% CIs will be presented.

12.5.2.1.2. Overall Survival

Overall survival is defined as the time from date of randomization to the date of death due to any cause. Kaplan-Meier curves and KM estimates of OS will be presented for each treatment arm,

including estimates of the median and other quantiles, as well as individual time points (eg, 3-, 6-, and 12-month rates). The log-rank test stratified by the randomization factors will be used to compare OS between the 2 treatment arms. The HR of OS with a 95% CI comparing the AG-120 + azacitidine arm with the placebo + azacitidine arm will be estimated from a Cox proportional hazards model stratified by the randomization stratification factors.

12.5.2.1.3. Complete Remission Plus Complete Remission With Partial Hematologic Recovery Rate

The CR + CRh rate is defined as the proportion of subjects who achieved a CR or CRh. CRh is defined as a CR with partial recovery of peripheral blood counts (< 5% bone marrow blasts, ANC $>0.5 \times 10^9/L$ [500/ μ L], and platelets $>50 \times 10^9/L$ [50,000/ μ L]). Because CRh is not part of modified IWG criteria, it will be derived by the Sponsor. A CMH test will be used to compare the CR + CRh rate between the 2 treatment arms. A logistic regression model will be used to estimate the treatment effect in terms of an odds ratio. The odds ratio and its associated 95% CIs will be presented.

12.5.2.1.4. Objective Response Rate

Objective response rate is defined as the rate of CR, CRi (including CRp), PR, and MLFS. The best response is calculated using the following hierarchy: 1) CR; 2) CRi (including CRp); 3) PR; and 4) MLFS. A summary of best response by treatment arm will be produced. A CMH test will be used to compare ORR between the 2 treatment arms. A logistic regression model will be used to estimate the treatment effect in terms of an odds ratio. The odds ratio and its associated 95% CIs will be presented.

12.5.2.2. Additional Secondary Endpoint Analyses

12.5.2.2.1. Complete Remission and CRi (Including CRp) Rate

The CR + CRi (including CRp) rate is defined as the proportion of subjects who achieved a CR or CRi (including CRp). A CMH test will be used to compare the CR + CRi (including CRp) rate between the 2 treatment arms. A logistic regression model will be used to estimate the treatment effect in terms of an odds ratio. The odds ratio and its associated 95% CIs will be presented.

12.5.2.2.2. DOCR, DOCRh, DOR, and DOCRI

Among subjects who achieved CR, DOCR will be calculated as the date of the first occurrence of CR to the date of first documented disease relapse, or death.

Among subjects who achieved CR or CRh, DOCRh will be calculated as the date of the first occurrence of CR or CRh to the date of first documented disease relapse or death.

Among subjects who achieved CR, CRi (including CRp), PR, and MLFS, DOR will be calculated as the date of the first response to the date of first documented disease relapse, disease progression, or death.

Among subjects who achieved CR or CRi (including CRp), DOCRI will be calculated as the date of the first occurrence of CR or CRi (including CRp) to the date of the first documented relapse or death.

Kaplan-Meier methods will be used to estimate DOCR, DOCRh, DOR, and DOCRi; subjects without relapse, disease progression, or death, as appropriate, at the time of analysis will be censored at the last response assessment date. Kaplan-Meier estimates of DOCR, DOCRh, DOR, and DOCRi will be presented by treatment arm, including estimates of the median and other quantiles, as well as individual time points (eg, 3-, 6-, and 12-month rates).

Subjects will be censored for DOCR, DOCRh, DOR, or DOCRi at the time of the start of subsequent anticancer therapy, should it occur prior to any DOCR, DOCRh, DOR, or DOCRi event, as appropriate. Detailed censoring rules will be included in the SAP. Kaplan-Meier estimates of DOCR, DOCRh, DOR, and DOCRi will be presented by treatment arm, including estimates of the median and other quantiles, as well as individual time points (eg, 3-, 6-, and 12-month rates).

12.5.2.2.3. TTCR, TTCRh, TTR, and TTCRi

Among subjects who achieved CR, TTCR will be assessed from the date of randomization to the date of first occurrence of CR.

Among subjects who achieved CR or CRh, TTCRh will be assessed from the date of randomization to the date of first occurrence of CR or CRh.

Among subjects who achieved CR, CRi (including CRp), PR, and MLFS, TTR will be assessed from the date of randomization to the date of the first response.

Among subjects who achieved CR or CRi (including CRp), TTCRi will be assessed from the date of randomization to the date of first occurrence of CR or CRi (including CRp).

Time to CR, TTCRh, TTR, and TTCRi will be summarized by treatment arm. Time to CR, TTCRh, TTR, and TTCRi will be presented by treatment arm using descriptive statistics.

12.5.2.2.4. Additional Clinical Benefit

Transfusion requirements (platelet and RBC; number of units), rates of infection, days spent hospitalized, and other efficacy and safety measures that are potentially indicative of clinical benefit will be summarized by treatment arm using descriptive statistics.

12.5.2.2.5. Quality of Life Assessments

Quality of life, as measured by EORTC QLQ-C30, will be evaluated for subjects with a baseline assessment and at least 1 post-baseline QLQ-C30 assessment that generate a score. For total QLQ-C30, each domain score (eg, physical functioning, role functioning, emotional functioning, cognitive functioning, social functioning), as well as symptom scales, baseline values, and change from baseline for each time point will be summarized by treatment arm using descriptive statistics. Mixed models will also be applied and the details will be specified in the SAP.

Health economic measures, as assessed by the EQ-5D-5L, will be evaluated for subjects with a baseline assessment and at least 1 post-baseline EQ-5D-5L assessment that generate a score. Scores at baseline and change from baseline scores for each time point will be quantified with descriptive statistics by treatment arm.

12.5.2.2.6. Evaluation of IDH1 Mutation Clearance

Complete remission with IDH1 MC is defined as a response of CR where there is no evidence of the IDH1 mutation by molecular techniques to below the level of detection (0.02%-0.04%) for ≥ 1 on-treatment time point. A CMH test will be used to compare the rate of CR with IDH1 MC between AG-120 + azacitidine and placebo + azacitidine. A logistic regression model will be used to estimate the treatment effect in terms of an odds ratio. The odds ratio and its associated 95% CIs will be presented.

12.6. Exposure and Safety Analyses

Safety will be evaluated by vital signs, the results of ECOG PS, ECG, and ECHO or MUGA for LVEF as clinically indicated (method per institutional standard of care, with the same method used for an individual subject throughout the study; sites in Germany may only use ECHO), clinical laboratory assessments (hematology, chemistry, and coagulation), and assessment of AEs, AESIs, SAEs, AEs leading to discontinuation or death, and concomitant medication use. All safety data will be listed by subject and summarized by treatment arm.

Clinically significant physical examination findings are captured as AEs will be listed by subject.

Concomitant medications will be listed by subject and will be summarized by treatment arm.

A summary of study drug exposure, including number of doses administered, total dose, duration of treatment, dose intensity, and the proportion of subjects with dose modifications, will be summarized by treatment arm. Reasons for dose modifications will be listed by subject and summarized.

12.6.1. Adverse Events

Summary tables for AEs will include any AE that occurs between the first dose of any study drug and 28 days following the last dose of any study drug. The incidence of AEs (new or worsening from baseline) will be summarized according to (Medical Dictionary for Regulatory Activities [MedDRA]) by system organ class and/or preferred term, severity (based on NCI CTCAE version 4.03 grading as assessed by the Investigator; see Appendix 15.9), seriousness, and relation to study treatment. The following summaries will be produced:

- All AEs
- Treatment-related AEs
- Grade ≥ 3 AEs
- Grade ≥ 3 treatment-related AEs
- The most commonly reported AEs (ie, those events reported in $\geq 10\%$ of all subjects)
- SAEs
- Treatment-related SAEs
- AESIs
- Discontinuations due to AEs
- AEs leading to dose modifications

- On-treatment deaths

By-subject listings will be provided for on-treatment deaths (on-treatment is defined as the period starting from the first dose to 28 days after the last dose), AEs, AESIs, SAEs, and AEs leading to discontinuation of treatment.

12.6.2. Laboratory Abnormalities

For laboratory tests included in the NCI CTCAE version 4.03, laboratory data will be graded accordingly; a Grade 0 will be assigned for all non-missing values not graded as 1 or higher. For laboratory tests where grades are not defined by CTCAE, results will be graded by the low/normal/high classifications based on laboratory normal ranges.

The following summaries will be generated separately for hematology, chemistry, and coagulation studies:

- Descriptive statistics for the actual values and/or change from baseline of clinical laboratory parameters over time.
- Shift tables using CTCAE grades to compare baseline to the worst on-treatment value (for laboratory tests where CTCAE grades are not defined, shift tables using the low/normal/high/[low and high] classification to compare baseline to the worst on-treatment may be generated).
- Listing of all laboratory data with values flagged to show the corresponding CTCAE grades and the classifications relative to the laboratory normal ranges.

In addition to the above-mentioned tables and listings, graphical displays of key safety parameters, such as scatter plots of actual or change in laboratory tests over time or box plots may be specified in the SAP.

12.6.3. Other Safety Data

Descriptive statistics of ECOG PS over time will be summarized by frequency. Shift tables may be provided for ECOG PS from baseline to worst value of post-baseline assessments.

Additional safety analyses may be performed if deemed necessary.

12.7. Pharmacokinetic Analyses

A population PK approach will be performed to assess typical and individual subject PK parameters of AG-120. Descriptive statistics will be used to summarize AG-120 PK concentrations at different nominal time points across subjects.

12.8. Pharmacodynamic Analyses

Descriptive statistics will be used to summarize 2-HG concentrations at different nominal time points across subjects. The potential relationship between plasma exposure of AG-120 and plasma 2-HG levels will be explored with descriptive and graphical methods as appropriate.

For the subjects who have IDH1 mutation results from both local evaluation and central laboratories, the concordance between the 2 tests will be explored.

[REDACTED]

12.10. Interim Analyses

There are no interim analyses for efficacy planned for this study.

Safety data will be reviewed regularly by an IDMC to ensure the safety of the combination therapy. These reviews will occur after the first 6, 12, 24, and 36 subjects have completed 1 cycle of therapy or discontinued, whichever should occur first. Thereafter, safety reviews will be conducted approximately every 6 months until the study is unblinded for the analysis of the primary endpoint.

12.11. Procedures for Handling Missing, Unused, and Spurious Data

No imputation will be performed for missing data elements unless specified otherwise.

When tabulating AE data, partial dates will be imputed. Rules of imputation will be specified in the SAP. All response assessments occurring after documented confirmed relapse/progression maybe be listed and analyzed separately.

12.12. Sample Size Estimation

A total of approximately 200 subjects with previously untreated IDH1m AML will participate in this study.

Assumptions for the placebo + azacitidine arm in this study are based on results from Study AZA-AML-001 in newly diagnosed AML patients who are ineligible for intensive IC receiving AG-120 in combination with azacitidine. Preliminary data from Study AZA-AML-001 were obtained under a data exchange agreement with Celgene. Based on results from a retrospective analysis of these data, the CR rate at 24 weeks is assumed to be 20% for the placebo + azacitidine arm. For subjects who achieve CR by 24 weeks, the median EFS is assumed to be 14.6 months. Assumptions for the AG-120 + azacitidine arm in this study are based on results from Study AG-221-AML-005 in newly diagnosed AML patients who are ineligible for intensive IC receiving AG-120 in combination with azacitidine. The CR rate by 24 weeks is

assumed to be 40%. For subjects who achieve CR by 24 weeks, a target HR of 0.76 for EFS (equivalent to a median EFS among responders of 14.6 months in the placebo + azacitidine arm vs 19.2 months in the AG-120 + azacitidine arm, assuming an exponential distribution) is assumed. Based on simulation results, the average overall HR over 10,000 simulations for the entire population is 0.641. Given that the assumption of proportional hazards is not met based on the EFS definition, the overall HR is less meaningful in this context. Therefore, the overall HR for the entire population was not part of the study design assumptions.

Under these assumptions, a total of 173 EFS events are required to provide 80% power at a 1-sided alpha of 0.025 level of significance to reject the null hypothesis using a stratified log-rank test. Assuming a recruitment period of approximately 44 months, with an accrual rate of 3 subjects per month during the first 10 months and 5 subjects per month thereafter, along with an assumed 5% overall dropout rate, approximately 200 subjects will be randomized to the 2 treatment arms in a 1:1 ratio. Given the above assumptions, it is estimated that the analysis of the primary endpoint for EFS will occur approximately 52 months after the first subject is randomized.

12.13. Power for Analysis of Key Secondary Endpoints

12.13.1. Power for Analysis of Overall Survival

Overall survival will be compared between the 2 treatment arms, provided the primary endpoint of EFS is statistically significant favoring the AG-120 + azacitidine arm. Based on available data ([Dombret et al, 2015](#)), the median OS in the placebo + azacitidine arm is expected to be approximately 10.4 months. A target HR of 0.71 for OS (equivalent to a median OS of 10.4 months in the placebo + azacitidine arm vs 14.6 months in the AG-120 + azacitidine arm, assuming an exponential distribution) is assumed. Based on the 200 subjects planned to be enrolled in this study to detect the primary endpoint of EFS, it is estimated that at the time of the final analysis for EFS, approximately 145 deaths will be observed and this will provide 54% power at a 1-sided overall 2.5% level of significance to reject the null hypotheses (HR=1) using a log-rank test.

12.13.2. Power for Analysis of Complete Remission Rate, Complete Remission Plus Complete Remission with Partial Hematologic Recovery Rate, and Objective Response Rate

Based on a retrospective analysis of Study AZA-AML-001, the response rates in the placebo + azacitidine arm are expected to be approximately 20%, 25%, and 32% for CR rate, CR + CRh rate, and ORR, respectively. It is hypothesized that the AG-120 + azacitidine arm will result in an absolute 20% increase in the CR rate, CR + CRh rate, and ORR. Based on the 200 subjects planned to be enrolled in this study to detect the primary endpoint of EFS, the power for the analysis of each of these endpoints at a 1-sided 2.5% level of significance to reject the null hypotheses (odds ratio=1) using a CMH test are presented in [Table 13](#).

Table 13: Power for Analysis of CR Rate, CR + CRh Rate, and ORR

Endpoints	Number of Subjects	Target Response Rate (Azacitidine vs AG-120 + Azacitidine)	Power
CR rate	200	20% vs 40%	86%
CR + CRh rate	200	25% vs 45%	84%
ORR	200	32% vs 52%	81%

Abbreviations: CR = complete remission; CRh = complete remission with partial hematologic recovery; ORR = objective response rate; vs = versus.

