12.5. Efficacy Analyses

During treatment, response will be evaluated by the Investigator based on modified IWG Response Criteria for AML (see Section 10.8.1) to determine subject status and continuation on study treatment. These response assessments will be used for the analysis of all efficacy endpoints. Because CRh is not part of modified IWG response criteria, it will be derived by the Sponsor.

To control the overall Type 1 error rate at the 1-sided 2.5% level, the fixed sequence testing procedure (Westfall and Krishen, 2001) will be used to adjust for multiple statistical testing of the primary and key secondary efficacy endpoints.

These endpoints will be tested in the following order:

- EFS
- CR rate
- OS
- CR + CRh rate
- ORR

No control of the alpha level will be made for the other analyses. No interim analyses for efficacy are planned.

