Based on a retrospective analysis of Study AZA-AML-001, the response rates in the placebo+azacitidine arm are assumed to be 20%, 25%, and 32% for CR, CR+CRh, and OR, respectively.

Based on 200 randomized subjects, the power for the analysis of each of these endpoints at a 1-sided 2.5% level of significance to reject the corresponding null hypotheses using a Cochran-Mantel-Haenszel (CMH) test are presented in Table 4.

Table 4: Power for Analyses of CR, CR+CRh, and OR

Endpoints	Number of Subjects	Assumed Response Rate under the Alternative Hypothesis (Treatment vs Control)	Power
CR	200	40% vs 20%	86%
CR+CRh	200	45% vs 25%	84%
OR	200	52% vs 32%	81%

Abbreviations: CR = complete remission; CRh = complete remission with partial hematologic recovery; OR = objective response; vs = versus.

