7.7.2.3. Complete Remission Plus Complete Remission with Partial Hematologic Recovery

The CR+CRh rate is defined as the proportion of subjects who achieved a CR or CRh. CRh is defined as a CR with partial recovery of peripheral blood counts [$<5\%$ bone marrow blasts, ANC $>0.5 \times 10^9/L$ (500/ μ L), and platelets $>50 \times 10^9/L$ (50,000/ μ L)].

Since CRh is not part of modified IWG criteria, it will be derived by the Sponsor based on the following rules, for each individual assessment which is not CR.

- Bone marrow blast $<5\%$, and
- Closest ANC within ± 8 days $>0.5 \times 10^9/L$, and
- Closest platelet counts within ± 8 days $>50 \times 10^9/L$, and
- Assume negative if Auer rod is not reported, and
- Assume negative if extramedullary disease is not reported

For bone marrow blasts, bone marrow aspirate will be used as the primary source. If a bone marrow aspirate assessment is not available, a bone marrow biopsy assessment will be used.

For ANC or platelet count, if there are 2 values which have the same distance to the bone marrow assessment date (eg, one is 1 day prior and the other is 1 day after), the value from the earlier assessment date will be used.

If the primary analyses of EFS, CR and OS are statistically significant, a CMH test stratified by the randomization stratification factors will be used to compare the CR+CRh rate between the 2 treatment arms at 1-sided 2.5% level of significance. The odds ratio and its associated 95% CI will be presented.

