7.7.2.4. Objective Response

Objective response rate is defined as the rate of CR, CRi (including CRp), PR, and MLFS.

The best response is calculated using the following hierarchy: 1) CR; 2) CRi (including CRp); 3) PR; and 4) MLFS.

Frequency of subjects with best response of CR, CRi (including CRp), PR or MLFS will be tabulated by treatment arm.

If the primary analysis of EFS, CR, OS and CR+CRh are statistically significant, a CMH test stratified by the randomization stratification factors will be used to compare ORR between the 2 treatment arms at 1-sided 2.5% level of significance. The odds ratio and its associated 95% CI will be presented.

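### The 84% and 81% power given for CR+CRh and ORR are single-test figures; under the fixed sequence neither can be claimed more often than the 54% stated for OS

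*Protocol*

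**What the plan says.** Protocol 12.5 sets the multiplicity rule: "To control the overall Type 1 error rate at the 1-sided 2.5% level, the fixed sequence testing procedure" is used for the primary and key secondary endpoints. It continues "These endpoints will be tested in the following order", and lists EFS, CR rate, OS, CR+CRh rate and ORR. SAP 6.2.1 gives the same order.

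The SAP then writes out each gate. Section 7.7.2.2 tests OS only after EFS and CR. Section 7.7.2.3 opens the CR+CRh test with "If the primary analyses of EFS, CR and OS are statistically significant", and section 7.7.2.4 opens the ORR test with "If the primary analysis of EFS, CR, OS and CR+CRh are statistically significant".

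On power, protocol 12.13.1 expects about 145 deaths at the EFS analysis and says "this will provide 54% power at a 1-sided overall 2.5% level of significance". SAP 6.2.1 gives the same 54%. Protocol 12.13.2 introduces Table 13 as "the power for the analysis of each of these endpoints at a 1-sided 2.5% level of significance to reject the null hypotheses (odds ratio=1", and the table lists 86% for CR, 84% for CR+CRh and 81% for ORR. SAP Table 4 repeats the three values as "the power for the analysis of each of these endpoints at a 1-sided 2.5% level of significance to reject the corresponding null hypotheses". Neither table mentions a gate, and neither document gives a probability of success under the sequence.

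**The concern.** In a fixed sequence, a null hypothesis further down the list can be rejected only if every test above it has been significant. The tables describe the chance of rejecting each null as though that test were always performed. CR+CRh and ORR stand behind OS, the weakest test in the family, so their printed power is higher than the plan can deliver.

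The power section also treats gating unevenly. Protocol 12.13.1 makes the OS comparison conditional on EFS but leaves out CR, which 12.5 and SAP 7.7.2.2 also require. Section 12.13.2, directly below, states no condition at all. Someone reading only 12.13 would take CR+CRh and ORR to be well-powered, unconditional tests and would misjudge what the key secondary family is likely to conclude. Type I error is not affected.

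**Working it through.** **Inputs.** 100 subjects per arm and 1-sided alpha 0.025 (protocol 12.12). Response rates 20% vs 40%, 25% vs 45% and 32% vs 52% (Table 13). OS hazard ratio 0.71 with 145 deaths (12.13.1). EFS power 80% (12.12).

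**1. The plan's own figures.** For rates, power = Φ[(p2 − p1 − 1.96·SE0)/SE1], where SE0 = √(2·p̄(1 − p̄)/100), SE1 = √((p1(1 − p1) + p2(1 − p2))/100) and p̄ is the mean of the two rates.

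- CR: (0.20 − 1.96 × 0.0648)/0.0632 = 1.15, power 87.6% (stated 86%).
- CR+CRh: (0.20 − 1.96 × 0.0675)/0.0660 = 1.03, power 84.8% (stated 84%).
- ORR: (0.20 − 1.96 × 0.0698)/0.0684 = 0.92, power 82.2% (stated 81%).
- OS, Schoenfeld formula: (√145/2) × |ln 0.71| − 1.96 = 6.02 × 0.3425 − 1.96 = 0.10, power 54.1% (stated 54%).

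With 95 per arm, allowing for 5% dropout, the three rates give 85.9%, 82.9% and 80.3%. All stated values are reproduced within 2 points as stand-alone powers.

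**2. The ceiling.** A CR+CRh claim requires EFS, CR, OS and CR+CRh all to be significant. The probability of a joint event cannot exceed that of its least likely part, so P(claim CR+CRh) ≤ min(0.80, 0.86, 0.54, 0.84) = 0.54. ORR needs one more test, so P(claim ORR) ≤ P(claim CR+CRh) ≤ 0.54. This uses only the plan's figures. The gaps are 84 − 54 = 30 points and 81 − 54 = 27 points.

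**3. Below the ceiling.** The documents give no correlation between response and OS, so it has to be assumed. A patient-level simulation (3,000 trials per setting) used:

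- nested CR, CR+CRh and ORR from one latent variable;
- exponential EFS in CR responders with medians 14.6 and 19.2 months, and an event at randomization for the others;
- exponential OS with medians 10.4 and 14.6 months;
- the stated accrual, with cutoff at the 173rd EFS event and at least 6 months of follow-up (standing in for the SAP's 24 weeks);
- unstratified tests and no dropout.

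Taken singly, the simulated tests rejected in 81-83% (EFS), 88-89% (CR), 52-54% (OS), 84-85% (CR+CRh) and 83-84% (ORR) of trials, with about 144 deaths, close to the plan. Probability of success under the sequence, in percent:

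| Assumed latent correlation, response and OS | CR | OS | CR+CRh | ORR |
|---|---|---|---|---|
| 0 | 78.5 | 41.0 | 39.0 | 37.0 |
| 0.3 | 77.8 | 42.5 | 40.9 | 39.4 |
| 0.5 | 77.2 | 43.8 | 42.0 | 40.3 |
| 0.7 | 78.0 | 46.7 | 45.5 | 44.5 |
| 0.9 | 78.2 | 49.5 | 48.9 | 48.0 |
| Stated, single test | 86 | 54 | 84 | 81 |

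The Monte Carlo standard error is about √(0.45 × 0.55/3000) = 0.9 points. Responder EFS is drawn separately from OS, so the model does not force a death to end EFS.

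For reference, full independence of all tests would give 0.80 × 0.86 × 0.54 × 0.84 = 31% for CR+CRh and 0.31 × 0.81 = 25% for ORR. That is unrealistic, because EFS is itself built from CR.

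**The case against.** The strongest reply is that nothing has been miscalculated. The tables give power per test, which is a common way to report it, and every value reproduces. The order, the gates and the 54% are all disclosed, the last directly above Table 13, so a statistician can see the ceiling. The 200 subjects were chosen for EFS, so these powers set neither sample size nor alpha. CR is tested before OS, and odds ratios with confidence intervals for CR+CRh and ORR are planned in any case.

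All of that stands, and it makes this a matter of what the printed figures mean. It does not remove the point. Both tables speak of power to reject the nulls and carry no condition, while the neighbouring OS paragraph does carry one, and an incomplete one.

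The reply is also right about the simulated range. It rests on an assumed correlation and a simplified model. Its lower end, correlation 0, fits poorly with the plan: death is an EFS event, and the responders' median EFS (14.6 and 19.2 months) exceeds the overall median OS (10.4 and 14.6 months), so responders must on average live longer.

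A reader might go further and infer that, on the plan's own assumptions, CR+CRh and ORR are more likely than not never to be tested. The documents do not support that. Their figures alone bound the chance of reaching these tests at 54%, which is above one half; getting below one half needs the added correlation model.

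**Conclusion.** The concern holds as a statement about what the figures mean. The 84% and 81% are correct single-test powers, and they are not the probability that the plan yields a formal claim. That probability is at most 54% for both endpoints, given the plan's OS assumptions (hazard ratio 0.71, 145 deaths), with no assumption about correlation. With the EFS and CR gates it is about 39-49% for CR+CRh and 37-48% for ORR if the response-OS latent correlation lies between 0 and 0.9; those ranges are conditional on the model and are not figures from the plan. The same gating lowers OS from 54% to about 41-50% and CR from 86% to about 77-79%. It would be wrong to call Table 13 an arithmetic error, or to quote any single value within the ranges as the true chance of success.

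**What to change.** - In protocol Table 13, protocol 12.13.1 and SAP Table 4, label the present figures as single-test power.
- State beside the tables that a formal claim on CR+CRh or ORR cannot be more probable than the 54% for OS.
- Add the probability of success under the fixed sequence for CR, OS, CR+CRh and ORR. These values should come from the sponsor's own simulation model, with the response-survival correlation stated and varied. The SAP already reports 10,000 simulations for EFS, so this extends existing work. The figures above indicate size and are not text to insert.
- Correct protocol 12.13.1 to say that OS is tested only if both EFS and CR are significant, in line with 12.5 and SAP 7.7.2.2.

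The cost is a text change and a further simulation run. Test order, sample size, alpha and analyses do not change. The drawback is that the stated figures become less favourable.
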